## **Appendix 4. Pregnancy Precautions, Definition for Female of Childbearing Potential, and Contraceptive Requirements**

### **1) Definitions**

#### **a) Definition of Childbearing Potential**

For the purposes of this study, a female born subject is considered of childbearing potential following menarche until becoming post-menopausal, unless permanently sterile or with medically documented ovarian failure.

Women are considered to be in a postmenopausal state when they are  $\geq 54$  years of age with cessation of previously occurring menses for  $\geq 12$  months without an alternative cause.

Permanent sterilization includes hysterectomy, bilateral oophorectomy, or bilateral salpingectomy in a female subject of any age.

#### **b) Definition of Male Fertility**

For the purposes of this study, a male born subject is considered fertile after the initiation of puberty unless permanently sterile by bilateral orchidectomy or medical documentation.

### **2) Study Drug Effects on Pregnancy and Hormonal Contraception**

Data from clinical pharmacokinetic interaction studies of SOF have demonstrated that there is no reduction in the clinical efficacy of hormonal contraception. Non-clinical toxicity studies of SOF have demonstrated no adverse effect on fertility or embryo-fetal development.

Data from clinical pharmacokinetic interaction studies of VEL have demonstrated that there is no reduction in the clinical efficacy of hormonal contraception. Non-clinical toxicity studies of GS-5816 have demonstrated no adverse effect on fertility or embryo-fetal development.

However, the risks of treatment with SOF/VEL during pregnancy in humans have not been evaluated. Please refer to the latest version of the investigator's brochure for additional information.

### **3) Contraception Requirements for Female Subjects of Childbearing Potential**

The inclusion of female subjects of childbearing potential requires using at least an acceptable effective contraceptive measure. They must have a negative serum pregnancy test at Screening and a negative pregnancy test on the Baseline/Day 1 visit prior to randomization. A pregnancy test will be performed at the Post Treatment Week 4 visit. They must also agree to one of the following from Screening until 30 days of the last dose of SOF/VEL.

- Complete abstinence from intercourse of reproductive potential. Abstinence is an acceptable method of contraception only when it is in line with the subject's preferred and usual lifestyle.

Or

- Consistent and correct use of 1 of the following methods of birth control listed below.
  - Intrauterine device (IUD)
  - Intrauterine hormone-releasing system (IUS)
  - Tubal sterilization
  - Essure micro-insert system
  - Vasectomy in the male partner
  - Barrier methods (one female barrier and one male barrier must be used in combination)
    - Female barriers: Diaphragm with spermicide or Cervical cap with spermicide
    - Male barriers: Male condom (with or without spermicide)
  - Hormonal methods
    - Oral contraceptives (either combined or progesterone only)
    - Injectable progesterone
    - Implants of levonorgestrel or etonorgestrel
    - Transdermal contraceptive patch
    - Contraceptive vaginal ring

Female subjects must also refrain from egg donation and in vitro fertilization during treatment and until at least 30 days after the last dose of SOF/VEL.

#### **4) Contraception Requirements for Male Subjects**

During the study, male subjects with female partners of childbearing potential should use condoms until 30 days after the last dose of SOF/VEL treatment when engaging in intercourse of reproductive potential. If their female partner is of childbearing potential (as defined above), their female partner must use 1 of the methods of birth control listed above from the date of Screening until 30 days after the last dose of SOF/VEL.

Male subjects must agree to refrain from sperm donation until 30 days after the last dose of SOF/VEL.

## **5) Unacceptable Methods of Contraception**

Birth control methods that are unacceptable include periodic abstinence (e.g., calendar, ovulation, symptothermal, post-ovulation methods), withdrawal (coitus interruptus), spermicides only, and lactational amenorrhea method (LAM). Female condom and male condom should not be used together.

## **6) Procedures to be Followed in the Event of Pregnancy**

Subjects will be instructed to notify the investigator if they become pregnant at any time during the study, or if they become pregnant within 30 days of the last dose of SOF/VEL. Subjects who become pregnant or who suspect that they are pregnant must report the information to the investigator and discontinue study drug immediately. Subjects whose partner has become pregnant or suspects she is pregnant must report the information to the investigator.

Instructions for reporting pregnancy, partner pregnancy, and pregnancy outcome are outlined in Section [7.6.2.1](#).

SOF	Sofosbuvir
SVR	sustained virologic response
SVRx	sustained virologic response x weeks after stopping all study drugs
TE	treatment-emergent
TFLs	tables, figures, and listings
TND	target not detected
ULN	upper limit of the normal range
VEL	Velpatasvir
VF	virologic failure
WBC	white blood cell
WHO	World Health Organization

1. INTRODUCTION

This statistical analysis plan (SAP) describes the statistical analysis methods and data presentations to be used in tables, figures, and listings (TFLs) for the clinical study report (CSR) for Study GS-US-342-2083. This SAP is based on the original protocol dated 26 February 2016 and the electronic case report form (eCRF). The SAP will be finalized before data finalization. Any changes made after the finalization of the SAP will be documented in the CSR.

1.1. Study Objectives

The primary objectives of this study are as follows:

- To explore the antiviral efficacy of treatment with sofosbuvir/velpatasvir (SOF/VEL) fixed-dose combination (FDC) therapy administered for 4 weeks following liver transplantation as measured by sustained virologic response (SVR) 12 weeks after cessation of treatment (SVR12)
- To evaluate the safety and tolerability of SOF/VEL in hepatitis C virus (HCV)-infected subjects in the perioperative and posttransplant period

The secondary objectives of this study are as follows:

- To determine the proportion of subjects who attain SVR at 4 weeks after cessation of therapy (SVR4)
- To evaluate the proportion of subjects with virologic failure (VF)
- To assess rates of graft survival, graft function, acute rejection and immunosuppressive therapy during treatment with SOF/VEL
- To evaluate the emergence of viral resistance to SOF and VEL during treatment and after cessation of treatment
- To evaluate the kinetics of circulating HCV RNA during treatment and after cessation of treatment
- To characterize pharmacokinetics of SOF/VEL

The exploratory objectives of this study are as follows:

The logo for PPD (Pfizer Inc.) is displayed in large, bold, black letters on a light blue background.

1.2. Study Design

This is an open-label study that will evaluate the safety, tolerability and antiviral efficacy of SOF/VEL administered for 4 weeks in HCV–infected adult male and non-pregnant/non-lactating female subjects 18 years of age or older who are undergoing liver transplantation. A detailed list of inclusion and exclusion criteria can be found in Sections 4.2 and 4.3 of the study protocol.

Screening assessments will be completed at the time the subject is identified as a potential participant for the study in order to allow the subject time to provide informed consent and to perform screening procedures. Subject’s screening data will be confirmed in the pre-operative period (within 48 hours of the planned transplant) if the screening visit was conducted more than 48 hours prior to the start of the transplant. If a separate consent is signed for the liver explant substudy, samples of the explanted liver will be taken during surgery.

For all subjects, SOF/VEL tablet (400/100 mg) once daily given orally or via nasogastric tube will be started the day of the subject’s liver transplant if the procedure is completed by noon and the following day if the transplant is completed after noon. Study personnel will observe the subject taking their first dose of study drug and record the date and time the first dose was taken.

The subject will receive treatment for 4 weeks. Treatment initiation may be delayed for up to 1 day if warranted by the subject’s medical condition post-surgery.

All subjects will complete the following study visits: screening, pre-surgery (if screening was conducted more than 48 hours prior to start of liver transplant), on-treatment Days 1, 3, 5, 7, 14, 21, and 28, and posttreatment Weeks 1, 2, 4, and 12 following last dose of study drug.

Pharmacokinetic (PK) Sub-study (Required)

All subjects will participate in a PK substudy in which intensive serial PK sample collection (samples obtained over 24 hours) will be performed on Day 1 to determine pharmacokinetics of SOF, its metabolites GS-566500 and GS-331007, and VEL.

The schedule of assessments can be found in Appendix 2 of the study protocol.

Subjects will be initially screened to determine their eligibility for participation in the study. Subjects will have an additional pre-surgery visit if the screening visit was conducted more than 48 hours prior to the start of liver transplant (ie, duration of screening period is variable depending on availability of a donor organ).

Subjects will be treated for 4 weeks and followed off-treatment for 12 weeks. All subjects will be eligible to participate in the PG substudy if consent is obtained. A blood sample should be drawn at the Day 1 visit. If not obtained at the Day 1 visit, the sample may be drawn at any time during the study.

Subjects with VF (either at end of treatment or during follow-up) will have a confirmation sample collected. If VF is confirmed, the subject will be discontinued from study.

Subjects who prematurely discontinue from study drug but complete all posttreatment visits will be considered to have completed study.

1.3. Sample Size

A total of 10 subjects are expected to be enrolled, receive a transplant, and be dosed with SOF/VEL. With a sample size of 10 subjects, a 2-sided 95% exact confidence interval (CI) will extend at most 63% in length.

2. TYPE OF PLANNED ANALYSIS

2.1. Data Monitoring Committee Meetings

A data monitoring committee (DMC) will review the progress of the study and perform interim reviews of safety data. The initial meeting will occur after the first 5 subjects have completed the treatment period; a second meeting will occur after all subjects complete the treatment period. The DMC will provide recommendations, and determine whether the nature, frequency, and severity of adverse effects associated with study treatment warrant the early termination of the study in the best interests of the participants, whether the study should continue as planned, or the study should continue with modifications. The investigator, medical monitor/study director, study biostatistician, and a sponsor representative who is not involved with the conduct of the study will be members of the DMC.

The DMC's specific activities will be defined by a mutually agreed charter, which will define the DMC's membership, conduct and meeting schedule.

2.2. Final Analysis

After all subjects have completed the study (posttreatment Week 12 or prematurely discontinued from study), all outstanding data queries for the study have been resolved, and the database has been cleaned and finalized, the final analysis of the data will be performed.

3. GENERAL CONSIDERATIONS FOR DATA ANALYSES

Analysis results will be presented using descriptive statistics. For categorical variables, the number and percentage of subjects in each category will be presented; for continuous variables, the number of subjects [n], mean, standard deviation [SD], median, first quartile [Q1], third quartile [Q3], minimum, and maximum will be presented.

Data collected in the study will be presented in by-subject listings for all subjects in the Safety Analysis Set, unless otherwise specified. All by-subject listings will be presented by subject identification (ID) number in ascending order, unless otherwise specified.

3.1. Analysis Sets

Analysis sets define the subjects to be included in an analysis. Analysis sets and their definitions are provided in this section. The number of subjects eligible for each analysis set will be provided. Subjects who were excluded from each analysis set will be summarized or provided in a by-subject listing with reasons for exclusion by treatment group.

3.1.1. All Enrolled Analysis Set

The All Enrolled Analysis Set includes subjects who were enrolled into the study (ie, subjects assigned a 5-digit subject ID). Subjects will be grouped by assigned treatment at enrollment (SOF/VEL 4 Weeks).

3.1.2. Full Analysis Set

The Full Analysis Set (FAS) includes all enrolled subjects who received a liver transplant, and took at least 1 dose of study drug. Since all subjects enrolled in this study received a liver transplant and took at least 1 dose of study drug, the FAS will be the same as the Safety Analysis Set.

This is the primary analysis set for efficacy analyses.

3.1.3. Safety Analysis Set

The Safety Analysis Set includes all subjects who took at least 1 dose of study drug. Subjects are grouped within the Safety Analysis Set according to the treatment they actually received.

This is the primary analysis set for safety analyses.

3.1.4. Pharmacokinetic Substudy Analysis Set

The Pharmacokinetic (PK) Substudy Analysis Set includes all subjects who took a dose of SOF/VEL on Study Day 1, and for whom PK parameters of the analytes of interest (SOF, its metabolites GS-566500 and GS-331007, and VEL) could be calculated based on intensive PK samples collected on Study Day 1 after the first posttransplant dose of SOF/VEL.

The PK Substudy Analysis Set will be used for analyses of the intensive PK data collected on study Day 1.

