#### 8.2.1.3. Pharmacokinetics

The PK analysis set will include subjects who were enrolled and received at least one dose of study drug, and have at least one nonmissing postdose concentration value for the corresponding analyte (VEL, SOF and its metabolite[s], as appropriate) in serum or plasma. The PK analysis set will be used for general analyses of PK.

The PK Substudy analysis set will include all subjects who were enrolled in the PK Substudy, have been administered at least one dose of study drug, and have at least one nonmissing postdose concentration value for the corresponding analyte (VEL, SOF and its metabolite[s], as appropriate) in serum or plasma. The PK Substudy analysis set will be used for intensive PK profiles of these analytes.

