When the HCV RNA IU/mL is less than LLOQ of the assay, the result is reported as “< 15 IU/mL.” This result will be referred to in this document as “< LLOQ detected.”

The overall category of HCV RNA < LLOQ includes “< LLOQ TND” and “< LLOQ detected.”

For numerical HCV RNA data, values below LLOQ will be set to the LLOQ – 1 IU/mL (ie, 14 HCV RNA IU/mL). HCV RNA values returned as “target not detected” will also be set to LLOQ – 1 IU/mL. For selected analyses, HCV RNA data (IU/mL) will be transformed to the logarithmic (base 10) scale (\log_{10} IU/mL).

If methods based on the assumption that the data are normally distributed are not adequate, analyses may be performed on transformed data (eg, \log_{10} scale) or nonparametric analysis methods may be used, as appropriate.

Natural logarithm transformation will be used for plasma/blood concentrations and analysis of PK parameters. Plasma concentration values that are below the limit of quantitation (BLQ) will be presented as “BLQ” in the concentration data listing. Values that are BLQ will be treated as 0 at predose time points, and one-half the value of the LOQ at postbaseline time points, where LOQ is corrected for the dilution factor (ie, reported LOQ/dilution factor) for determination of summary and order statistics.

The following conventions will be used for the presentation of summary and order statistics:

- If at least 1 subject has a concentration value of BLQ for the time point, the minimum value will be displayed as “BLQ.”
- If more than 25% of the subjects have a concentration data value of BLQ for a given time point, the minimum and Q1 values will be displayed as “BLQ.”
- If more than 50% of the subjects have a concentration data value of BLQ for a given time point, the minimum, Q1, and median values will be displayed as “BLQ.”
- If more than 75% of the subjects have a concentration data value of BLQ for a given time point, the minimum, Q1, median, and Q3 values will be displayed as “BLQ.”
- If all subjects have concentration data values of BLQ for a given time point, all order statistics (minimum, Q1, median, Q3, and maximum) will be displayed as “BLQ.”

Pharmacokinetic parameters that are BLQ will be imputed as one-half LOQ before log transformation.

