8.2.2. Pharmacokinetic Parameters

Pharmacokinetic parameters will be generated for all subjects in the PK substudy analysis set based on intensive PK samples collected on Study Day 1.

The pharmacokinetic parameters for VEL, SOF, GS-566500 and GS-331007 will be computed for all subjects with evaluable PK profiles. For each subject, the following PK parameters will be calculated, as appropriate:

Table 3. Pharmacokinetic Parameters for Each Analyte

Parameter	Description
AUC ₀₋₂₄	area under the concentration versus time curve over the dosing interval
AUC _{last}	area under the concentration versus time curve from time zero to the last quantifiable concentration
C _{last}	last observed quantifiable concentration of the drug in plasma
C _{max}	maximum observed concentration of drug in plasma
C ₂₄	observed drug concentration at the end of the dosing interval
t _{1/2}	estimate of the terminal elimination half-life of the drug in plasma, calculated by dividing the natural log of 2 by the terminal elimination rate constant (λ_z)
T _{last}	time (observed time point) of C _{last}
T _{max}	time (observed time point) of C _{max}
λ_z	terminal elimination rate estimated by linear regression of the terminal elimination phase of the plasma concentration of drug versus time curve

Individual subject concentration data at each timepoint, and individual subject PK parameters for VEL, SOF, and SOF metabolites GS-566500 and GS-331007 in plasma will be listed and summarized using descriptive statistics (n, mean, SD, coefficient of variation [%CV], median, min, max, Q1, and Q3) by route of SOF/VEL administration (PO or NG) on Study Day 1. In addition, for individual subject PK parameter data, the geometric mean, 95% CI, and the mean and SD of the natural log-transformed values will be presented.

Individual concentration data listings and summaries (intensive PK) will include all subjects with concentration data. The sample size for each time point will be based on the number of subjects with nonmissing concentration data at that time point. The number of subjects with concentration BLQ will be presented for each time point. For summary statistics, BLQ values will be treated as 0 at predose and one-half of the lower limit of quantitation (LLOQ) for the analyte being summarized at postdose time points, where LLOQ is corrected for the dilution factor (ie, reported dilution/dilution factor).

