Individual PK parameter data listings and summaries will include all subjects for whom PK parameter(s) can be derived. The sample size for each PK parameter will be based on the number of subjects with nonmissing data for that PK parameter.

The following tables will be provided for each analyte by route of SOF/VEL administration (PO or NG) and overall on study Day 1:

- Individual subject concentration data and summary statistics
- Individual subject plasma PK parameters and summary statistics

The following figures may be provided for each analyte by SOF/VEL route of administration (PO or NG) on Study Day 1:

- Mean (\pm SD) concentration data versus time (on linear and semilogarithmic scales)
- Median (Q1, Q3) concentration data versus time (on linear and semilogarithmic scales)

Mean and median postdose concentration values that are \leq LLOQ will not be displayed in the figures and remaining points connected.

The following listing will be provided:

- PK sampling details (and PK concentrations) by subject that includes both intensive and sparse PK samples

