29.7*	Neutrophils ($\times 10^3/\mu\text{L}$) by Visit	Safety Analysis Set
29.8*	Lymphocytes ($\times 10^3/\mu\text{L}$) by Visit	Safety Analysis Set
29.9*	Reticulocyte Count ($\times 10^3/\mu\text{L}$) by Visit	Safety Analysis Set
29.10*	Hemoglobin (g/dL) by Visit	Safety Analysis Set
29.11*	Platelets ($\times 10^3/\mu\text{L}$) by Visit	Safety Analysis Set
29.12*	Albumin (g/dL) by Visit	Safety Analysis Set
29.13*	INR by Visit	Safety Analysis Set
29.14*	Serum Creatinine (mg/dL) by Visit	Safety Analysis Set
29.15*	Creatinine Clearance (mL/min)	Safety Analysis Set
30	Postbaseline Hemoglobin < 10 g/dL and < 8.5 g/dL	Safety Analysis Set
31.1	Pulse (bpm) by Visit	Safety Analysis Set
31.2	Diastolic Blood Pressure (mmHg) by Visit	Safety Analysis Set
31.3	Systolic Blood Pressure (mmHg) by Visit	Safety Analysis Set

* Included in DMC analysis.

PK Table or Figure Number	Title	Analysis Set
PK Table 1	Subjects Evaluable by Study Day 1 SOF/VEL Route of Administration	PK Substudy Analysis Set
PK Table 2	Plasma SOF Concentrations (ng/mL) by Subject with Summary Statistics for Each Substudy Timepoint (by Route of SOF/VEL Administration on Day 1)	PK Substudy Analysis Set
PK Table 3	Plasma GS-331007 Concentrations (ng/mL) by Subject with Summary Statistics for Each Substudy Timepoint (by Route of SOF/VEL Administration on Day 1)	PK Substudy Analysis Set
PK Table 4	Plasma GS-566500 Concentrations (ng/mL) by Subject with Summary Statistics for Each Substudy Timepoint (by Route of SOF/VEL Administration on Day 1)	PK Substudy Analysis Set
PK Table 5	Plasma VEL Concentrations (ng/mL) by Subject with Summary Statistics for Each Substudy Timepoint (by Route of SOF/VEL Administration on Day 1)	PK Substudy Analysis Set
PK Table 6	Plasma SOF Pharmacokinetic Parameters by Subject with Summary Statistics for Each Parameter (by Route of SOF/VEL Administration on Day 1)	PK Substudy Analysis Set
PK Table 7	Plasma GS-331007 Pharmacokinetic Parameters by Subject with Summary Statistics for Each Parameter (by Route of SOF/VEL Administration on Day 1)	PK Substudy Analysis Set
PK Table 8	Plasma GS-566500 Pharmacokinetic Parameters by Subject with Summary Statistics for Each Parameter (by Route of SOF/VEL Administration on Day 1)	PK Substudy Analysis Set
PK Table 9	Plasma VEL Pharmacokinetic Parameters by Subject with Summary Statistics for Each Parameter (by Route of SOF/VEL Administration on Day 1)	PK Substudy Analysis Set

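### The SAP's PK Substudy Analysis Set is narrower than the protocol's and conflicts with SAP 8.2.2, so all-BLQ profiles may drop out of the intensive PK tables

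*SAP*

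**What the plan says.** Protocol 8.2.1.3 builds the PK Substudy set from substudy subjects who "have been administered at least one dose of study drug, and have at least one nonmissing postdose concentration value for the corresponding analyte". Membership is therefore settled analyte by analyte.

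SAP 3.1.4 replaces this with "all subjects who took a dose of SOF/VEL on Study Day 1, and for whom PK parameters of the analytes of interest" could be computed from the Day 1 intensive samples. It names SOF, GS-566500, GS-331007 and VEL in one list joined by a single conjunction. It then says: "The PK Substudy Analysis Set will be used for analyses of the intensive PK data collected on study Day 1".

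SAP 8.2.2 sets two other rules. For concentrations: "Individual concentration data listings and summaries (intensive PK) will include all subjects with concentration data". For parameters: "Individual PK parameter data listings and summaries will include all subjects for whom PK parameter(s) can be derived", with n counted separately for each parameter. The same section opens by generating parameters for members of the PK Substudy set.

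In the SAP appendix, PK Tables 2-5 (for VEL, titled "Plasma VEL Concentrations (ng/mL) by Subject with Summary Statistics for Each Substudy Timepoint") and PK Tables 6-9 (parameters) are all assigned to the PK Substudy Analysis Set. PK Listing 1 is assigned to a PK Analysis Set that the SAP does not define.

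On values below the limit of quantitation, SAP 3.7 says: "Pharmacokinetic parameters that are BLQ will be imputed as one-half LOQ before log transformation". Protocol 8.3 has the same rule.

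**The concern.** Under the SAP a subject enters the analysis set only if the result permits a calculation, so membership depends on the outcome being described. The SAP does not explain the change. It has change-from-protocol entries for efficacy (6.4) and safety (7.8), but none for PK.

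Characterizing PK is a secondary objective. SOF/VEL starts straight after transplant, protocol 5.2 allows the tablet to be crushed and given by nasogastric tube, and SAP 3.2 splits the PK results into oral, nasogastric and overall. With about 10 subjects, the route groups are small and one omission can move a summary. A subject in whom an analyte is never quantified is among the more informative cases for that comparison, and is the one most clearly exposed to the narrower rule.

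**Working it through.** **The plan's own figure.** The plan gives no figure for this point. The only design figure is the exact 95% interval length of at most 63% for 10 subjects. It reproduces (5 of 10: 18.7% to 81.3%, width 62.6%) and supplies only N = 10.

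**Step 1: who is in which set.** A reported BLQ result is taken as a nonmissing value, since both documents assign it half the limit in postdose summaries.

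| Profile | Protocol 8.2.1.3 | SAP 3.1.4 | SAP 8.2.2 |
|---|---|---|---|
| Every postdose sample BLQ for an analyte | In | Out on the plain reading | In for concentrations; parameters not settled |
| One quantifiable sample per analyte | In | In, unless every parameter is required | In for both |
| Three analytes calculable, one not | In for each analyte with a postdose value | Out altogether if all four are required | In for concentrations; in for the parameters that exist |

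**Step 2: what a poor profile still yields.** Illustrative profiles were put on the planned times (0, 0.5, 1, 2, 4, 8, 12, 24 h) with the SAP 8.2.1 rules: linear up/log down, BLQ before the first quantifiable value set to 0, later BLQ missing. Concentrations are in units of LOQ. At least three points after Tmax are assumed necessary for the terminal slope.

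- One quantifiable value (1.5 at 4 h): Cmax 1.5, AUClast = 2 h × 1.5/2 = 1.5. Tmax, Clast and Tlast also exist; the terminal slope and half-life do not.
- Three quantifiable values (1.2, 2.0, 1.4 at 2, 4, 8 h): Cmax 2.0, AUClast = 0.6 + 3.2 + 6.73 = 10.53. Again only the slope and half-life fail.
- Still rising at 24 h (1, 3, 6, 9 at 4, 8, 12, 24 h): Cmax 9, AUClast = 1 + 8 + 18 + 90 = 117. The slope and half-life fail here too.
- All BLQ: nothing quantifiable to compute from.

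So low exposure alone does not exclude a subject. Requiring every parameter would also remove a well-absorbed late-peak profile.

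**Step 3: size if someone is dropped.** Let k of N subjects be dropped, with exposure a fraction f of the others'. The mean after exclusion, relative to the mean with everyone, is

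- arithmetic: N / (N − k + kf)
- geometric: (1/f)^(k/N)

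The values of k and f and the route-group size of 5 are assumptions. For k = 1:

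| f | N = 10, arithmetic | N = 10, geometric | N = 5, arithmetic | N = 5, geometric |
|---|---|---|---|---|
| 0 | 10/9 = 1.11 | undefined | 5/4 = 1.25 | undefined |
| 0.01 | 10/9.01 = 1.11 | 100^0.1 = 1.58 | 5/4.01 = 1.25 | 100^0.2 = 2.51 |
| 0.1 | 10/9.1 = 1.10 | 10^0.1 = 1.26 | 5/4.1 = 1.22 | 10^0.2 = 1.58 |
| 0.5 | 10/9.5 = 1.05 | 2^0.1 = 1.07 | 5/4.5 = 1.11 | 2^0.2 = 1.15 |

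The top rows fit an all-BLQ profile. The lower rows matter mainly if all four analytes are required. With k = 0 every ratio is 1.

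**The case against.** The strongest reply is that SAP 8.2.2 already does what is asked. It puts every subject with concentrations into the concentration summaries, sets postdose BLQ to half the limit and shows BLQ counts at each time point. It also covers parameters, with n per parameter, and the wording and the per-analyte tables weigh against requiring all four analytes. A parameter that cannot be derived is missing under the protocol's set too. SAP 3.1 promises that exclusions from each analysis set will be summarized or listed with reasons, and PK Listing 1 shows concentrations by subject. Protocol 8.7 leaves PK detail to a separate plan, which is not among these documents.

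Most of this stands, and it makes the point small. It does not remove the conflict. The restricted set is tied to the intensive PK analyses by the text of 3.1.4 itself, not only by table labels. The parameter rule is circular: 8.2.2 generates parameters for members of a set that is defined by having parameters. The exclusions listing in the appendix (Listing 2.1) covers only the Safety and Full Analysis Sets.

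Two stronger readings are tempting. A reader might infer that poor absorbers are selected out and exposure is therefore overstated. The documents do not support that: one quantifiable sample yields Cmax and AUClast, no excluded subject is documented, and a profile may be unusable because of missed samples or a late peak, so direction and size are unknown. A reader might also infer that the half-LOQ rule for parameters becomes idle. It does not, because C24 can be BLQ in a subject whose other parameters are calculable.

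**Conclusion.** The inconsistency is on the page; its numerical effect is conditional. Followed through 3.1.4 and the table list, the SAP would drop an all-BLQ profile that the protocol keeps. If all four analytes are required, it would also drop a subject with one non-calculable analyte. Followed through 8.2.2, the concentration summaries would lose nobody.

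If one subject with near-zero exposure were dropped, the arithmetic mean would be overstated by 11% with N = 10, or by 25% in a route group of 5 (assumed size). The geometric mean, which the SAP also reports for parameters, is more sensitive: 1.58-fold and 2.51-fold if that subject has 1% of the others' exposure (assumed). That comparison needs a positive value for the dropped subject, and the documents do not give the assay limits that would fix it. If nobody is excluded there is no bias. Severity: minor.

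**What to change.** 1. Restore the protocol's analyte-by-analyte definition in SAP 3.1.4.
2. Run PK Tables 2-5 on all subjects with any postdose concentration, as SAP 8.2.2 already intends.
3. Keep n per parameter in PK Tables 6-9.
4. Keep all-BLQ profiles visible by counting them by analyte and route. Apply half-LOQ only to concentration-type parameters (Cmax, C24). It is not a valid AUC value, because AUC is concentration times time. One option for AUC is to set AUClast to 0 in arithmetic summaries, extending the SAP 8.2.1 rule for BLQ samples before the first quantifiable value, and to state the number of such subjects beside the geometric mean.
5. List exclusions from the PK set with reasons, as SAP 3.1 promises, and show the route.
6. Define the PK Analysis Set named in PK Listing 1, or replace it with a defined set.

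The cost is SAP wording and table footers. If all-BLQ profiles occur, mean exposures will be somewhat lower and more variable.
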